#### III. Methods and Measures

#### A. Design

The Meals for Moms study is a pilot study to test the feasibility and acceptance of using continuous glucose monitors to measure changes in glucose associated with providing medically tailored meals to postpartum women who had gestational diabetes. A schematic of study enrollment, intervention design, and follow-up is included in Figure 1.

#### B. Setting

The Meals for Moms pilot study is a collaborative partnership between researchers and clinicians from Wake Forest Baptist Medical Center and Providence Community Kitchen, a subsidiary of the Second Harvest Foodbank of Northwest North Carolina.

#### C. Subjects selection criteria

The principles guiding the selection of the following inclusion and exclusion criteria are to ensure the enrollment of participants who meet 2 major criteria: 1) high risk for future adverse health outcomes due to the diagnosis of GDM and excessive GWG; and 2) no medical contraindications to participate in a medically tailored meal program. Participants will include 30 women in the third trimester of a singleton pregnancy or who have recently given birth (within the previous 14 days) who

Figure 1. Schematic of Study Participation

receive obstetric care at a Wake Forest Baptist Health clinic and reside in Forsyth County, NC.

#### Inclusion Criteria

• Demographics: Women 18 years of age and older who reside in Forsyth County, NC

- Pregnancy: Currently 24 or more weeks into a singleton pregnancy or who have given birth within the past 14 days
- Clinical evidence of GDM defined as either:
  - 3-hour oral glucose tolerance test (OGTT) results obtained in the second trimester of pregnancy that show at least 2 abnormal values in any of the following combinations:
    - Fasting glucose > 95 mg/dL and 1h > 180 mg/dL
    - Fasting glucose > 95 mg/dL and 2h > GE 155 mg/dL
    - Fasting glucose > 95 mg/dL and 3h > 140 mg/dL
    - 1h > 180 mg/dL and 2h > 155 mg/dL
    - 1h > 180 mg/dL and 3h > 140 mg/dL
    - 2h > 155 mg/dL and 3h > 140 mg/dL
  - A diagnosis of "gestational diabetes" included on the Problem List in Wake One during current pregnancy, regardless of OGTT values
- Pre-gravid overweight or obesity or excessive GWG: Overweight or obese (BMI ≥25.0 kg/m^2) prior to current pregnancy OR most recent weight exceeds predicted weight gain for current weeks gestational age based on starting BMI defined as:
  - Pre-pregnancy BMI of 30 kg/m^2 or more and weight at most recent clinical visit 20+ pounds over pre-pregnancy weight
  - Pre-pregnancy BMI of 25-29.9 kg/m^2 and weight at most recent clinical visit 25+ pounds over pre-pregnancy weight
- English Proficiency: Able to read/understand English at or above a level sufficient to comprehend recruitment, informed consent, and intervention materials.
- Access to a smart phone/tablet/computer capable of connecting to video calls or teleconferencing software.
- Access to freezer space to store 10 frozen meals delivered to the home each week.
- Willingness to Accept Treatment Assignment: Prospective participants must be willing to accept assignment to either the medically tailored meal intervention or the comparison intervention condition.

### Exclusion Criteria

- Clinical history of diabetes (type 1 or 2) pre-pregnancy
- Non-singleton pregnancy
- Other chronic diseases or medical conditions that would increase risk or make participation otherwise unsafe, including special dietary needs. A clinician investigator will review the medical record for all potential participants to determine if any such conditions exist.
- Known food allergies or sensitivities. Potential participants who report special dietary requirements including vegetarians, vegans, those who follow kosher or other specialized diets will be excluded due to the small nature of this pilot study.
- History of allergic skin reaction to adhesive tape
- Unable or unwilling to wear a CGM device
- Is scheduled for an MRI during the study weeks, making use of the CGM device unsafe
- Other: Conditions/criteria likely to interfere with participation and acceptance of treatment group assignment, including the following: inability/unwillingness to give informed consent, major psychiatric or cognitive problems (schizophrenia, dementia, self-reported substance or alcohol abuse), participation in another research study that would interfere with Meals for Moms

### D. Sample Size

We anticipate recruiting a sample of 30 women (12 African-American, 10 Hispanic, 8 Non-Hispanic White). This is a pilot study and is not powered to test the effect of the MTM intervention on any outcome. The

estimates obtained in this study will be used to design a fully powered randomized controlled trial assessing the effect of a post-partum MTM intervention on blood glucose. Estimates of retention and adherence will be used to modify the sample size to account for dropouts and poor adherence. Estimates of the participation and accrual rates will be used to judge the feasibility of the subsequent trial given the required sample size relative to patient availability and our ability to recruit them into our trial.

#### E. Screening and Enrollment

We will generate weekly datasets using the Clarity reporting relational database in WakeOne to identify potentially eligible women within the electronic health record (EHR). The EHR data pulls will identify women, age 18 years or older, in their third trimester of pregnancy seen for obstetric care in a WFBH clinic in the past week who had a diagnosis of GDM with excessive GWG, and for whom English is the documented primary language. Datasets of up to 50 women who meet these criteria will be output weekly to a secure folder on the PHS network which only IRB-approved study staff may access. Datasets will also include patient name, age, MRN, expected delivery date, pre-gravid height and weight (to calculate BMI), current weight, diagnosis of GDM, and OGTT results. Research staff will then access individual EHR data to identify contact information and will place a telephone call to potential participants to discuss the study and to assess additional eligibility criteria. As we anticipate that some women who meet eligibility criteria may not appear in these datasets until very close to their expected delivery date and may not be reached for recruitment pre-partum, we will also attempt to contact women who appear in the dataset who have recently given birth (within the past 14 days). Additionally, a physician investigator will review diagnostic codes associated with recent encounters for all potential participants to identify any potential diagnoses or health conditions that may make participation unsafe or increase risk, including diagnosis of Type 1 or Type 2 diabetes pre-pregnancy, cardiovascular disease, essential hypertension, and dyslipidemia.

Potential participants who 1) satisfy the inclusion/exclusion criteria previously described, and 2) indicate that they are willing to provide written informed consent will be invited to complete a virtual baseline visit and be enrolled in the study. Informed consent will be obtained at the beginning of this visit (see Section I.b. Informed Consent for details). Given current patient volumes, we anticipate recruiting 1-2 women per week over a period of 3-4 months. As the study timeline is brief, 20

participants will be recruited into a MTM treatment group to ensure the feasibility of the intervention approach is tested. If sufficient time remains, an additional 10 participants will be recruited into a usual care comparison condition.

After enrollment, participants will be routinely monitored via the EHR to determine when they are admitted for delivery and to check for any potential problems during the delivery. To standardize anticipated contacts across all participants, the Estimated Date of Delivery (EDD) will be used to schedule meal deliveries, mailings, and email contacts for both treatment groups. Our plan is to initiate participant data collection post-partum within 2 weeks of delivery. Study staff will contact the participant approximately one week after the EDD to check on delivery status. We will also collect contact information during the enrollment process for an alternative contact person in

Table 1. Outline of Weekly Video Emails

Week	Video
1	The 4th Trimester (St. Louis Children's Hospital video)
2	HELP -Mindfulness
3	HELP - ABCs of emotions
4	Phone visit with study team (no email)
5	HELP - Tipping the calorie balance
6	HELP - Healthy Eating
7	HELP - More About Healthy Eating
8	Phone visit with study team (no email)
9	HELP - Physical Activity 101
10	HELP - Problem solving
11	HELP - Creating an environment for success
12	Phone visit with study team (no email)

the case of negative outcomes during or after delivery. Study staff will make at least five (5) attempts by phone, email, or text message to reach enrolled participants or their alternate contacts in the 2 weeks following the EDD. Continuous glucose monitors, readers, daily diaries, digital scales, and informational materials about the study and healthy diet resources will be delivered to participants by mail after the participant has been reached and continued participation is

confirmed. Those participants who do not respond to study contact after delivery

or who decline further participation will not receive study-related materials or meal delivery and will be considered as drop-outs. For those participants who are recruited and enrolled after giving birth, data collection will begin from the date of recruitment and informed consent.

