### H. Analytical Plan

Since this pilot study is primarily about feasibility, analysis will be limited. We will describe baseline characteristics including demographics and cardiometabolic risk factors by CGM metrics. We will use mixed models with a random subject effect to estimate change in glucose metric variables across follow up with adjustment for demographics and other relevant confounders of dysglycemia. We will assess differences in CGM metric changes between participants receiving the MTM intervention and controls with independent sample t-tests. We will conduct similar analysis for change in weight.

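### The usual-care group is conditional and, as described, not randomised, yet the groups are compared by unadjusted t-tests, and neither the difference nor the MTM-only change is ruled out as a design input for the next trial

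*Combined protocol and SAP*

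**What the plan says.** **Recruitment (Section III.E).** Because the timeline is short, 20 "participants will be recruited into a MTM treatment group to ensure the feasibility of the intervention approach is tested". The next sentence is: "If sufficient time remains, an additional 10 participants will be recruited into a usual care comparison condition". On accrual: "we anticipate recruiting 1-2 women per week over a period of 3-4 months".

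**Allocation.** The inclusion criteria (Section III.C) require each woman to be prepared to take either condition. No section describes a random or other allocation method. The enrolment step in Section III.I issues an ID only. The word randomised is used only for the future trial, in Section III.D.

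**Analysis (Section III.H).** Change over time: "We will use mixed models with a random subject effect to estimate change in glucose metric variables across follow up", adjusted for demographics and confounders; no group or group-by-time term is named. Between groups: "We will assess differences in CGM metric changes between participants receiving the MTM intervention and controls with independent sample t-tests", with no covariates. Then: "We will conduct similar analysis for change in weight".

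**Use of the results (Section III.D).** "We anticipate recruiting a sample of 30 women". The section disclaims power for the MTM effect on any outcome, and says that the "estimates obtained in this study will be used to design a fully powered randomized controlled trial". It goes on to give specific uses for retention, adherence, participation and accrual.

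**The concern.** The groups are formed by something other than chance, apparently by when a woman enrols and whether time is left. An unadjusted t-test on change treats them as exchangeable, and nothing in the design makes them so. The requirement to accept either assignment could lead a reader to assume randomisation.

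One concrete route to imbalance is baseline timing. Women enrolled after birth start data collection at consent, so if the mix of antenatal and postnatal enrolment differs between groups, so does the time since delivery at the first CGM.

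The feasibility objective is not affected. What is at stake is the second objective in Section II, preliminary effectiveness, whose primary measure is 3-month change in CGM markers. Followed as written, the plan can produce a confounded difference with a p-value, and nothing in Section III.D keeps that difference out of the design of the next trial.

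The change in the MTM group alone is no safer. Section I.B says that weight generally falls fastest in the first half-year after birth, and that metabolic disturbances of pregnancy mostly either clear or become persistent by about 12 weeks. Change over the study's 3 months can be expected without the meals.

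**Working it through.** **The plan's own figure.** 20 + 10 = 30, which matches Section III.D, as does its breakdown by race and ethnicity (12 + 10 + 8 = 30). There is no power calculation to reproduce: no alpha, power, SD or effect size is given.

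**How many controls?** Inputs are the 1–2 women per week and 3–4 months of Section III.E, with MTM filled first. Weeks = months × 52/12, giving 13.0 and 17.3. Enrolled = rate × weeks. Controls = enrolled − 20, limited to 0–10. The rate of 1.5 is an intermediate value for illustration.

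| Rate per week | Enrolled, 3 months | Controls | Enrolled, 4 months | Controls |
|---|---|---|---|---|
| 1 | 13.0 | 0 (MTM short by 7.0) | 17.3 | 0 (MTM short by 2.7) |
| 1.5 | 19.5 | 0 | 26.0 | 6 |
| 2 | 26.0 | 6 | 34.7 | 10 |

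Thirty women need 15 weeks at 2 per week, which is inside the stated range but near its top. The required rate is 30/17.3 = 1.73 per week over 4 months, and 30/13.0 = 2.31 over 3 months, which exceeds the stated maximum.

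**How precise is the difference?** In units of the SD of change, half-width = t(0.975, n1 + n2 − 2) × √(1/n1 + 1/n2).

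- 20 vs 10: 2.048 × 0.387 = 0.79
- 20 vs 6: 2.064 × 0.465 = 0.96
- 20 vs 3: 2.080 × 0.619 = 1.29

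Section III.E foresees drop-outs but gives no rate. Assuming 10–30% in both groups, 20 vs 10 becomes 18 vs 9 to 14 vs 7, with half-widths of 0.84 to 0.97.

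**What could non-exchangeability do to the test?** The documents give neither size nor direction, so this is an assumed range. Suppose the meals have no effect, but the groups' expected changes differ by 0.25, 0.5 or 0.75 SD in either direction. With 20 vs 10, 28 degrees of freedom, an assumed two-sided 5% level and noncentrality = difference/0.387, the t-test rejects in 9.6%, 23.9% or 46.4% of studies instead of 5%.

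**Does the existing adjustment help?** Not as written. The adjusted mixed model estimates change across follow-up, and the group comparison is a separate sentence with a separate, unadjusted method. If there are no controls, the t-test cannot be run and Section III.H names no fallback, although within-group change can still be estimated.

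**The case against.** The strongest reply is that this is a pilot that says so. It disclaims power, calls its effectiveness aim exploratory, limits its analysis, and spells out only feasibility quantities as inputs to the next trial. Much of that stands, and it rules out several stronger readings that a reader might infer.

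- **That the sponsor plans to size the next trial on the group difference.** Section III.D does not say this. Its lead sentence is merely unrestricted.
- **That the bias will flatter the meals and leave the next trial too small.** Nothing supports a direction or a size. A bias against MTM would have the opposite effect.
- **That the groups are separated in calendar time.** Women may enrol from 24 weeks of pregnancy to 14 days after birth, so delivery and CGM dates can overlap. Overlap weakens a calendar effect but does not make the groups exchangeable.
- **That baseline timing could differ without limit.** Postnatal enrolment stops at 14 days, and the plan aims for baseline within 2 weeks of delivery, so the intended shift is at most about two weeks.
- **That staff select women knowing which group is open.** This is an inference; the protocol does not say so, and the requirement to accept either group limits self-selection.
- **That 30 women cannot be reached.** They can, within the stated accrual range.

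It is also fair to say that even a randomised 20 vs 10 comparison, with a standard error of 0.39 SD, would be a poor basis for an effect size. That supports excluding the estimate rather than leaving the text alone. The reply fails on one point: lack of power is a statement about precision. No section acknowledges that the comparison is non-randomised.

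**Conclusion.** The point holds as a matter of what the text says and omits. No allocation method is described, controls are conditional on time, the between-group test is unadjusted, and neither the difference nor the MTM-only change is excluded from the next trial's design. Enrolment of controls after MTM is the natural reading of Section III.E, not its explicit wording.

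The size of the problem is known only in part. The difference would carry a half-width of 0.79 SD at best and 0.96 SD with six controls, before drop-out, and at the lower accrual rates there would be no controls at all. The bias itself cannot be sized, and misuse of the estimate is possible rather than planned. This should be corrected, but it does not threaten the feasibility aims.

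**What to change.** 1. **Section III.H.** Replace the between-group t-tests, for CGM metrics and weight, with an estimate and 95% confidence interval from the mixed model already planned, with group and group-by-time terms. Add a small number of covariates already collected, for example days postpartum at baseline CGM, obtainable from the delivery date and the sensor placement date in the Appendix C diary. Enter each covariate by time as well: with two complete measurements per woman, a main effect alone leaves the difference in change unadjusted. Label the result non-randomised and descriptive, with no significance test. If no controls are enrolled, report the MTM change only and do not attribute it to the meals.

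2. **Section III.D.** State that neither the group difference nor the MTM-only change will set the effect size of the next trial. Estimates of SD, retention, adherence and accrual may be used.

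3. **Section III.E.** State that assignment is not randomised, say how it is made, and say that usual-care participants may number from 0 to 10.

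**Cost.** This is a wording amendment; recruitment order and MTM numbers do not change. The pilot gives up a between-group p-value, and the adjusted estimate will be imprecise with at most 30 women. Adjustment for a few covariates reduces confounding but cannot remove it, so the label matters as much as the model.

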B. The Postpartum Period: A Opportunity to Improve Maternal Metabolic Health Most cardiometabolic perturbations from pregnancy will either resolve or persist within 12 weeks after delivery. Further, the first 6 months after a baby is born are generally the period of most rapid weight loss for new mothers. Weight plateau and even regain typically occur by 12 months postpartum, with consequences for short and long-term glycemic control. Despite the opportunity to improve women's cardiometabolic health trajectories during the early postpartum period, many aspects of traditional weight loss and glycemic control interventions, such as intensive in-person visits and meal planning/preparation are quite difficult to implement and sustain while caring for a newborn infant. Attendance rates at postpartum clinical visits are low,  only 50% for Medicaid patients,  exemplifying the fact that new mothers have limited bandwidth for self-care activities. Postpartum dysglycemia & weight retention pose both an opportunity and a challenge for primary and secondary prevention of obstetric and cardiometabolic outcomes in women.

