### BMI 50+ - 2000 kcal daily

- Breakfast 200-300 kcal
- Mid-morning snack: 200 kcal
- Lunch (provided most days) 450-600 kcal
- Mid-Afternoon snack (on own) 200 kcal

- Dinner (provided most days) 450-600 kcal
- After-dinner snack: 200 kcal

As described previously, study staff will run weekly EHR reports to identify when a participant is admitted to the hospital for delivery. About one week post-EDD, a member of the study team will contact the participant via text or phone call to ensure that she has delivered and is still planning to participate. We will coordinate with the participant and/or other household member to initiate home delivery of MTMs within 2 weeks (14 days) of delivery.

			Visit	
Primary Measures or Constructs	Screening	Baseline	Intervention	Follow-Up
Study evaluation of acceptability				х
Process measures				х
CGM		Х		х
Secondary Measures of Constructs				
Maternal and infant anthropometrics		х	х	х
Rapid Eating Assessment for Participants (REAP-S)		х		х
Food Insecurity		х		х
Awareness of GDM, management		х		
Diet-related comorbidities	х			
Infant feeding plans and practice		х		х
Financial stress		х		
Overall stress		х		
Confusion Hubub and Order Scale (CHAOS)		х		
Plans for weight-loss		х		
Health literacy		х	х	
Social support		Х		х
Data collection for recruitment and retention				
Pregnancy, delivery history		X		
OGTT	X			
Demographics		X		

Once per week, for a period of 3 months, 10 MTM (5 lunches and 5 dinners) portioned to feed one adult and frozen for ease of storage will be delivered directly to the participant's home by Providence Kitchen staff. MTM deliveries will include reheating instructions and recipe cards with nutritional information. During the monthly phone visits with a member of the study team, participants in the MTM treatment group will also be given the opportunity to provide feedback on the weekly meal delivery, food preparation, and troubleshoot any potential issues with this component of the intervention.

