### G. Measures

Measures in this study have been selected to reflect the feasibility, acceptability, and preliminary effectiveness objectives of this pilot study and include participant self-reported constructs, existing medical history and pregnancy history information from the EHR, and data collected directly via CGM. A table outlining the time points at which each measure is collected and the mode of collection is included in Table 3.

Demographics: We are collecting self-reported data on gender, race, ethnicity, highest level of education, marital status, and the number of adults and children living in the home.

Continuous Glucose Monitoring: Participants will wear a blinded FreeStyle Libre Pro CGM at baseline (first 2 weeks after delivery) and at follow up (after 3 months). CGM devices will be mailed to participants and a member of the study team will video call participants to provide instructions and real time guidance on attachment and activation of the CGM. In order to facilitate collecting baseline post-partum CGM data and weight, this call will occur as close to the actual date of delivery as is possible. The participants will wear the CGM for 14 days at the beginning (initial month) and end (3 months) of the study. They will also keep a daily diary of the timing of meals, sleeping, and exercise (Appendix C). Study staff will call participants on day 14 to remind them to remove the sensor and provide instructions and guidance if needed for removal. At the conclusion of the 3 months, an abbreviated remote virtual visit to aid in placement and activation of the second continuous glucose monitor will be conducted. Participants will return the continuous glucose monitors, readers, and daily diaries to the study coordinator by mail using prepaid mailers. A 1-page report with a summary of the 14-day glucose data (graph of glucose values with information on the normal range) will be provided back to participants together with a cover letter for them to share with their health care provider if they choose.

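### For women enrolled before birth, contact and mailings run from the due date while the baseline window runs from delivery, so an early delivery pushes the baseline CGM and weight past 2 weeks if the schedule is followed as written

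*Combined protocol and SAP*

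**What the plan says.** Two clocks are in use for women enrolled before birth.

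**Clock 1, the due date.** Section III.E (Screening and Enrollment) states that "the Estimated Date of Delivery (EDD) will be used to schedule meal deliveries, mailings, and email contacts for both treatment groups". It continues: "Study staff will contact the participant approximately one week after the EDD to check on delivery status". Attempts to reach participants or "their alternate contacts in the 2 weeks following the EDD" follow. Monitors, readers, diaries and scales "will be delivered to participants by mail after the participant has been reached and continued participation is" confirmed. Section III.F.a (MTM Intervention, after the calorie lists) describes weekly EHR reports that identify admission for delivery, and then repeats the due-date rule: "About one week post-EDD, a member of the study team will contact the participant via text or phone call".

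**Clock 2, actual delivery.** Section III.E also says: "Our plan is to initiate participant data collection post-partum within 2 weeks of delivery". Section III.G (Continuous Glucose Monitoring) says: "Participants will wear a blinded FreeStyle Libre Pro CGM at baseline (first 2 weeks after delivery"). Section III.G (Anthropometrics) places the first maternal weight within 2 weeks of delivery, on the mailed scale. Section III.F.a aims to start meals within 14 days of delivery.

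Two further statements in III.G bear on the point. The sensor-placement call is to be made as near to the actual delivery as can be managed, and the first wear is also described, more loosely, as falling in the initial month of the study. Women enrolled after birth start data collection at consent, so they are not on the EDD clock.

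**The concern.** The kit needed for both baseline measurements is released by a contact timed from the EDD, but the measurements are due by a date counted from delivery. The two agree only when delivery is close to or after the EDD. The earlier the delivery, the later after it the baseline falls.

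This matters because the 3-month change in CGM markers is the primary effectiveness measure (section II), and change in weight is analysed in the same way (section III.H). Section I.B says: "Most cardiometabolic perturbations from pregnancy will either resolve or persist within 12 weeks after delivery". If glucose and weight are moving over those weeks, a baseline taken at different postpartum days captures different amounts of the natural course. That adds variation to the change scores that has nothing to do with the meals. Section III.H names no adjustment for postpartum day, and the between-group t-tests have no covariates. Section III.D says the estimates will be used to design the full trial, so the extra variation would carry forward.

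**Working it through.** The plan gives no figure of its own to reproduce. The check is calendar arithmetic.

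**Inputs**
- d = days by which delivery precedes the EDD.
- c = contact, in days after the EDD: about 7 (III.E, III.F.a). Because the plan says approximately, 5 is also tried. The attempts run to 14 (III.E).
- m = mailing time in days. The documents do not give it; 0, 3 and 5 are assumed.
- Window: closes on postpartum day 14 (III.E, III.G).
- Wear: 14 days (III.G).

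**Formulas**
- Postpartum day of first contact = d + c.
- Postpartum day of sensor start = d + c + m.
- Largest d that still allows a start by day 14 = 14 − c − m.

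**Contact at EDD + 7**

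| Days early (d) | Contact day | Sensor start, m = 3 | Sensor start, m = 5 |
|---|---|---|---|
| 0 | 7 | 10 | 12 |
| 3 | 10 | 13 | 15 |
| 5 | 12 | 15 | 17 |
| 7 | 14 | 17 | 19 |
| 14 | 21 | 24 | 26 |
| 21 | 28 | 31 | 33 |

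**Largest d with a start by day 14**

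| Contact | m = 0 | m = 3 | m = 5 |
|---|---|---|---|
| EDD + 5 | 9 | 6 | 4 |
| EDD + 7 | 7 | 4 | 2 |
| EDD + 14 | 0 | −3 | −5 |

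At EDD + 7 the contact alone uses up the window when delivery is 7 days early. With 3 to 5 days of mailing and contact at EDD + 5 to EDD + 7, the limit is 2 to 6 days early, or about 4. If the woman is reached only at EDD + 14, even delivery on the EDD leaves no time for mailing.

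**What the window can mean.** A full 14-day wear inside the first 14 days needs a start on day 14 − 14 = 0. With contact at EDD + 7 and m = 0 to 5, delivery on the EDD gives a wear that ends on day 7 + 14 = 21 to 12 + 14 = 26. The 2-week window can only sensibly refer to sensor start.

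**The initial-month wording.** Take a month as 28 days from delivery. If it refers to sensor start, deliveries up to 28 − 7 − 3 = 18 days early (m = 3) or 28 − 7 − 5 = 16 days early (m = 5) fit. If it refers to the whole wear, the start must be by day 28 − 14 = 14, which is the same limit as the 2-week window.

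**Delivery-based trigger.** A weekly report adds at most 7 days. With r days to reach the woman (not given), the start is by day 7 + r + m: 10 + r with m = 3, or 12 + r with m = 5. Day 14 is then met if r is at most 4 or 2 days. The start no longer depends on d.

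**The case against.** The strongest reply is that the plan does not ignore actual delivery. Staff monitor the EHR for admission, the placement call is meant to follow delivery closely, and nothing forbids earlier contact once a birth is known. Mailing depends on the woman being reached, not on the EDD having passed. A reader might infer that early deliverers cannot have a timely baseline. The documents do not support that, because staff could act on the EHR. What remains is that no sentence tells them to, and III.F.a describes the EHR report and then still times the contact from the EDD.

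Other parts of the reply also stand:
- The contact time is approximate, so 7 days is not a sharp cut-off.
- The initial-month wording, read as sensor start, would accommodate many of the later starts. It is also a second window that conflicts with the first.
- The EDD rule applies to both groups, so it does not by itself favour either one.
- The pilot is not powered and its analysis is deliberately limited.

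A reader might also infer that the rule makes early postpartum CGM look less feasible. The feasibility measures in sections II and III.G are completion of CGM collection, days worn, technical problems and adverse events. None is stated to require a start by day 14, so this is not shown. Mailing kits before the EDD may look like an easy remedy, but it would bypass the step in III.E that confirms continued participation after delivery.

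**Conclusion.** The inconsistency is real and should be corrected. If the EDD schedule is followed as written, delivery about 7 or more days early puts the baseline CGM and weight outside the 2-week target. Under the assumed 3 to 5 days of mailing, and allowing for the approximate contact time, the limit is about 4 days early. Sensor start moves one day later for each day that delivery is earlier.

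Two quantities cannot be given. The documents contain no distribution of delivery dates, so the share of women affected is unknown. They also give no time course for postpartum glucose, and section I.B says that perturbations resolve or persist, so any fraction of natural change lost before baseline would be invented. The supportable consequence is avoidable variation in baseline timing, related to gestation at delivery, in the primary effectiveness measure. The point does not concern women enrolled after birth.

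**What to change.** 1. In III.E and III.F.a, make the delivery recorded in the EHR report the trigger for contact, and for mailing the sensor, reader, diary and scale once continued participation is confirmed. Keep the call at about one week after the EDD as a back-up for women with no recorded delivery.
2. In III.G, state that the baseline window applies to sensor start, and reconcile the 2-week window with the initial-month wording, including the date from which the month is counted.
3. Record postpartum day at sensor start for each wear, and name it as a covariate in the mixed model of III.H. Enter it as the value at each wear: a single value per woman, entered only as a main effect, would shift her level but not her change. With 30 women the adjustment will be imprecise, so the distribution of baseline postpartum day should be reported as well.
4. Reconcile the EDD-based and delivery-based passages on the start of meals.

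The cost is protocol wording and one derived date. The EHR reports already run, and the confirmation step is kept.
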